3.12.3 Reproductive Toxicity

The potential for acalabrutinib to be excreted in breast milk of nursing mothers is unknown.

It is unknown whether venetoclax or its metabolites are excreted in human milk.

A risk to the breast-feeding child cannot be excluded.

Breast-feeding should be discontinued during treatment with venetoclax.

For results of acalabrutinib nonclinical reproductive toxicity studies, including definitive embryofetal development studies, please refer to the Investigator Brochure.

Women of childbearing potential (WOCBP) who are sexually active must use highly effective methods of contraception during treatment and for 30 days after the last dose of acalabrutinib. Please refer to the Investigator Brochure for detailed definitions for WOCBP and highly effective methods of contraception.

Women should avoid becoming pregnant while taking venetoclax and for at least 30 days after ending treatment. Therefore, women of childbearing potential must use highly effective contraceptive measures while taking venetoclax and for 30 days after stopping treatment. It is currently unknown whether venetoclax may reduce the effectiveness of hormonal contraceptives, and therefore women using hormonal contraceptives should add a barrier method.

No human data on the effect of venetoclax on fertility are available. Based on testicular toxicity in dogs at clinically relevant exposures, male fertility may be compromised by treatment with venetoclax (see section 5.3). Before starting treatment, counselling on sperm storage may be considered in some male patients.

Subjects should promptly notify the investigator if they, or their partner, become pregnant during this study, or within 30 days after the last dose of acalabrutinib and venetoclax. If a female subject becomes pregnant during the treatment period, she must discontinue acalabrutinib and venetoclax immediately. Pregnancy in a female subject or a male subject's partner must be reported as outlined in Section 6.2.4.

For women of childbearing potential a pregnancy test will be performed at screening. A negative pregnancy test is required for all WOCBP within 7 days before start of study treatment. If WOCBP is randomized to the treatment arm additional pregnancy tests will be performed at the visits C2D1, C3D1 and End of Treatment.

3.12.4 Overdose Instructions

Clinical information relevant to overdose is not available. For results from nonclinical overdose studies in rats and dogs, please refer to the Investigator Brochure.

There is no specific antidote for venetoclax. Patients who experience overdose should be closely monitored and appropriate supportive treatment provided. During dose-titration phase, treatment should be interrupted, and patients should be monitored carefully for signs and symptoms of TLS (fever, chills, nausea, vomiting, confusion, shortness of breath, seizures, irregular heartbeat, dark or cloudy urine, unusual tiredness, muscle or joint pain, abdominal pain and distension) along with

other toxicities (see section 4.2). Based on venetoclax large volume of distribution and extensive protein binding, dialysis is unlikely to result in significant removal of venetoclax.

Study drug overdose is the accidental or intentional use of the drug in an amount higher than the dose being studied. An overdose or incorrect administration of study drug is not an AE unless it results in untoward medical effects.

Any study drug overdose or incorrect administration of study drug should be noted on the appropriate CRF, for the sponsor to report to companies and health authorities according to EU regulations.

All AEs associated with an overdose or incorrect administration of study drug should be recorded on the CRF. If the associated AE fulfills serious criteria, the event should be reported to the companies per contractual guidelines.

In the event of subject ingestion of more than the recommended study drug dosage, observation for any symptomatic side effects should be instituted, and vital signs, biochemical and hematologic parameters should be followed closely (consistent with the protocol or more frequently, as needed). Appropriate supportive management to mitigate adverse effects should be initiated. If the overdose ingestion of acalabrutinib is recent and substantial, and if there are no medical contraindications, use of gastric lavage or induction of emesis may be considered.

3.13 WITHDRAWAL OF SUBJECTS FROM STUDY TREATMENT

The investigator may withdraw any subject from study treatment, if, in the investigator's opinion, it is not in the subject's best interest to continue.

Any subject has the right to withdraw from the study at any time. In addition, subjects may be withdrawn from study treatment for the following reasons:

- Study treatment should be discontinued in the event of a toxicity leading to pausing of any of the investigational drugs > 28 days, unless reviewed and approved by the sponsor.
- Any subject who starts new chemotherapy or chemoimmunotherapy for the treatment of CLL, becomes pregnant or breastfeeding, is significantly noncompliant according to the treating physician's assessment, etc. should be withdrawn from study treatment.

Subjects who discontinue study therapy will continue to be followed on study for follow-up of safety and survival unless they withdraw consent for further follow-up. Thus, all subjects receiving ≥ 1 dose of study drug will be followed during the immediate post-therapy and long-term follow-up assessments unless the subject withdraws consent for such follow-up to be conducted.

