3.4.2 Safety Parameters

Due to the pre-emptive treatment of a patient population normally not treated, an independent Data Safety Monitoring Board (DSMB) will assure ongoing assessment of infectious risk and adverse events. The trial may be stopped based on the decision by the independent DSMB if increased infectious risk or AE risk is considered to outweigh the potential benefit during enrollment. Extensive assessment of immune function including phenotyping of immune cells, cytokine profiling and functional assays of immune function will be performed along with assessment of MRD and subclonal development. Infections will be closely monitored for the first 2 years, thus

including the 18-months follow up. Follow up will be aligned for the treatment arm and the observation arm to avoid registration bias.

For consistency of interpretation, AEs and laboratory results will be coded using the Medical Dictionary for Regulatory Activities (MedDRA), and the severity of AEs will be graded using the Common Terminology Criteria for Adverse Events (CTCAE), Version 5. Standard definitions for seriousness will be applied.

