3.6.4 Enrollment and Randomization Procedures

The investigator assumes the responsibility of obtaining written informed consent for each patient for the treatment before any study-specific procedures and randomization is performed. A central medical review of the screening CRF pages and the results of the baseline results in the central laboratories will be performed by study physicians for verification of the eligibility of the patient, especially for confirmation of the CLL diagnosis.

Randomization has to occur within 42 days of the tests for screening, however results included for the CLL-TIM assessment, which were obtained as part of routine care for the patients may be included even prior to randomization. FISH analysis for cytogenetic aberrations and TP53 mutational assessment should be within 6 months of randomization. Patients will be randomly assigned to treatment vs observation through 1:1 randomization process with stratification

according to country, TP53 aberration status and IGHV mutational status. Treatment or observation period has to be initiated within 14 days of randomization.

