4.4 FOLLOW-UP FOR INFECTION, PROGRESSION AND SURVIVAL

4.4.1 Discontinuation Follow-up

Each subject should be followed until disease progression or the start of alternative CLL therapy and at least for the first two years after randomization. If neither of these has occurred at the time of the 2-year SFU visit, follow-up visits should occur approximately every 6 months until disease progression or next CLL treatment. During this period, subjects will be followed via out-patient clinic and/or registries per investigator discretion including registration of any infectious events.

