4.4.2 Long-Term Follow-up

Once subjects progress or start use of alternative CLL therapy—for all subjects who have not withdrawn consent — they will be contacted or followed approximately every 3 months by clinic visit, electronic assessment or telephone, to assess survival, the use of alternative CLL therapy and infections.

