5.3.4 Secondary Efficacy Endpoint

CLL-treatment-free survival (TFS), is defined as the time from first dose or start of observation to initiation of (another) CLL-treatment or death from any cause.

OS is defined as the time from first dose or start of observation to death from any cause. Data for subjects who are still alive at the time of data cutoff date, lost to follow-up, have discontinued the study (or, if no post-baseline assessment, at the time of first dose plus 1 day). Duration of OS will be estimated using Kaplan-Meier methodology. Approximate 95% CIs for median duration of OS will be computed using the formula proposed by Brookmeyer and Crowley.

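### TFS and OS are timed from first dose or start of observation instead of randomisation, so a randomised patient who never starts has no time zero

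*Protocol*

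**What the plan says.** **Start of the clock.** In 5.3.4, TFS "is defined as the time from first dose or start of observation to initiation of (another) CLL-treatment or death from any cause", and OS is the "time from first dose or start of observation to death from any cause". The sentence on OS censoring is incomplete, but its fallback for a patient without follow-up data reads "if no post-baseline assessment, at the time of first dose plus 1 day".

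**Gap before the clock starts.** Section 3.6.4: "Treatment or observation period has to be initiated within 14 days of randomization". This applies to both arms.

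**Other anchors on dose or start.** Section 3.13, on patients who stop study therapy, concludes that "all subjects receiving ≥ 1 dose of study drug will be followed during the immediate post-therapy and long-term follow-up assessments", unless they withdraw consent. Section 4.3 places the 2-year safety visit two years after first dose or observation. Section 6.1.1 opens the adverse event period at first dose in the treatment arm and at Cycle 1 Day 1 in the observation arm.

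**Anchor on randomisation.** Section 4.4.1: "Each subject should be followed until disease progression or the start of alternative CLL therapy and at least for the first two years after randomization". Section 4.4.2 continues after progression or alternative therapy "for all subjects who have not withdrawn consent". Section 3.4.2 adds: "Follow up will be aligned for the treatment arm and the observation arm to avoid registration bias".

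**The concern.** Randomisation makes the arms comparable on the day of allocation. Here the clock for two survival endpoints starts later, and at a different kind of event in each arm: swallowing a first dose in one, a nominal Cycle 1 Day 1 in the other. Treatment is open label and given to patients who do not meet criteria for needing it, so some may decline or become unable to start after allocation.

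Such a patient has no TFS or OS time under 5.3.4. The analyst must then improvise a date or leave the patient out. With 25 patients per arm, a choice made after the data are seen could matter. The adverse event window in 6.1.1 has the same gap, and infections are collected through it as events of special interest, so the problem is not confined to TFS and OS.

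**Working it through.** **1. Apply the definitions to each kind of randomised patient.**

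| Patient | Time zero for TFS and OS (5.3.4) | OS fallback date (5.3.4) | Adverse event period opens (6.1.1) | Follow-up (4.4.1) |
|---|---|---|---|---|
| Treatment, dosed | first dose | exists | first dose | at least 2 years from randomisation |
| Treatment, never dosed | none | none | never | at least 2 years from randomisation |
| Observation, started | start of observation | none, as there is no first dose | Cycle 1 Day 1 | at least 2 years from randomisation |
| Observation, leaves before Cycle 1 Day 1 | none | none | never | at least 2 years from randomisation, unless consent is withdrawn |

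Two things follow. The fallback date fails for the whole observation arm, whether or not anyone fails to start. And 4.4.1 covers every row, so the data would be gathered for patients whom 5.3.4 cannot place on a time axis.

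**2. Size of the gap in time.** At most 14 days per patient; against two years of close follow-up that is 14/730 = 1.9%. For infections, assume that the protocol's 10% in 6 months (about 182 days) accrues evenly and that every patient uses the full 14 days. Expected grade ≥3 infections before start are then 25 × 0.10 × 14/182 = 0.19 per arm.

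**3. Weight of one never-starter.** 1/25 = 4% of an arm; three would be 3/25 = 12%. The counts are assumptions, since the protocol states no rate.

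**4. Effect on power, using the only design figure given.** That figure is for the primary endpoint, not for TFS or OS: 10% in both arms, 25 per arm, 80% power, margin 21 points. Alpha is not stated; one-sided 5% reproduces it.
- SE = √(0.10 × 0.90/25 + 0.10 × 0.90/25) = 0.0849.
- Margin at 80% power = (1.645 + 0.842) × 0.0849 = 21.1 points, and power at 21 points is 79.7%. At one-sided 2.5% the margin would be 23.8 points, which does not match.
- If treatment-arm never-starters were lost from that arm alone: two lost gives 78.2%, three 77.3%, five 75.4%. The loss of power is small.

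**5. Effect on the estimate.** Let starters have a 10% event rate and k never-starters a rate q. The rate in the full treatment arm is [(25 − k) × 0.10 + k × q]/25. For k = 2:
- q = 0: 9.2%
- q = 0.3: 11.6%
- q = 0.5: 13.2%
- q = 1: 17.2%

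The shift can go either way, depending on a q that the protocol does not give.

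**6. Extreme illustration on the primary endpoint.** Suppose 2/25 events on observation and 2/23 among treatment-arm starters. The upper one-sided 95% Wald bound is 0.0070 + 1.645 × 0.0800 = 13.9 points, inside 21. If both never-starters had events and were counted, 4/25 gives 0.080 + 1.645 × 0.0912 = 23.0 points, outside. This shows only that two patients can decide the result at this sample size.

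**The case against.** The strongest reply is that the protocol already follows everyone. A reader might infer from 3.13 that follow-up is promised only to patients who took a dose. The documents do not support that. The sentence draws a consequence for patients who discontinue therapy; it includes the dosed and excludes nobody. Read as a condition for retention, it would shut out the entire observation arm. Section 4.4.1 counts from randomisation with no dose condition, 3.4.2 aligns the arms, and 3.14 does not list never starting as a reason for removal. This part of the reply stands in full.

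A reader might also infer that never-starters are dropped from the treatment arm alone, that observation loses nobody, and that the result therefore favours treatment. None of this is written. No section orders an exclusion, 5.2 keeps drop-outs in up to their last evaluation, and analysis sets may be defined in a statistical analysis plan that is not at hand. Observation has its own Cycle 1 Day 1, so a patient who leaves before it has the same gap, though that may be less likely. Bias towards treatment requires never-starters to do worse, and a patient who simply changes their mind need not.

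What the reply leaves untouched is the definition itself. Even an all-randomised analysis set, combined with 5.3.4 as written, has no start date for a patient who never starts.

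**Conclusion.** The point holds as a defect of definition and an inconsistency between sections. Section 5.3.4 leaves TFS and OS undefined for a treatment-arm patient who never takes a dose, counts no event between randomisation and start in either arm, and gives an OS fallback date that no observation patient can have. Sections 3.13, 4.3, 5.3.4 and 6.1.1 are tied to dose or start, while 4.4.1 is tied to randomisation.

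The certain part is small: at most 14 days per patient. The uncertain part depends on how many patients never start and how they fare. Each would be 4% of an arm; the number, their event rate and hence the direction of any bias are unknown. The documents do not show that patients are lost from one arm only, or that treatment is favoured. The case for a change rests on protecting the randomised comparison at very low cost.

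**What to change.** - **5.3.4:** define TFS and OS from the date of randomisation in both arms, analyse all randomised patients as allocated, and set the OS fallback censoring date to the date of randomisation plus 1 day.
- **3.13:** state that all randomised subjects are followed whether or not study drug or observation was started, consistent with 4.4.1, subject to consent.
- **6.1.1 and 4.3:** start collection of endpoint events, infections in particular, at randomisation, and count the 2-year visit from the same date.

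The primary endpoint in 5.3.3 currently names both start of treatment or observation and enrollment as its origin. It should be checked for consistency with the date chosen here.

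**Cost:** wording changes only. The randomisation date is already needed to apply the 14-day limit in 3.6.4. TFS and OS times lengthen by at most 14 days in both arms, and those days carry no drug exposure, so exposure-based safety summaries may still be counted from first dose.

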3.14 REMOVAL FROM STUDY

Reasons for removal of a subject from the study are:

- Subject's withdrawal of consent from study
- Decision by sponsor to terminate the trial
- Decision by the investigator or sponsor for safety reasons
- Subject lost to follow-up (for more than 2 years)
- Death

3.15 DATA AND SAFETY MONITORING

This trial will be monitored in accordance with the Sponsor's Pharmacovigilance procedures.

Adverse events, AESIs, and SAEs will be reviewed internally as part of ongoing safety surveillance and a DSMB will be monitoring the trial as detailed in later sections.

4. STUDY ACTIVITIES AND ASSESSMENTS

The schedule of events is provided in Appendix 1. Descriptions of the scheduled evaluations are outlined below and information on study drug and dosing is provided in section 3.4 and under each study drug description.

Before study entry, throughout the study, and at the follow-up evaluation, various clinical and diagnostic laboratory evaluations are outlined. The purpose of obtaining these detailed measurements is to ensure adequate safety and tolerability assessments. Clinical evaluations and laboratory studies may be repeated more frequently if clinically indicated.

4.1 DESCRIPTION OF PROCEDURES

4.1.1 Informed Consent

The subject must read, understand and sign the ICF approved by the institutional review board or independent ethics committee (IRB/IEC), confirming his or her willingness to participate in this study before initiating any screening activity that is not standard of care. Subjects must also grant permission to use protected health information, if required by local regulations in accordance with GDPR legislation. Subjects must also give permission that biobank material may be analyzed outside the EU.

The ICF will be in two parts, one for the screening part including obtaining information for the screening testing and the usage of data for CLL-TIM algorithm and assessment of risk of infection and/or treatment by the algorithm as well as follow up by medical record review and/or health registries and obtaining blood and other biological specimens for the adjoined research biobank.

The second part of the ICF will only be for patients assessed as high risk by the CLL-TIM algorithm, thus eligible for the clinical study including study procedures and randomization between treatment or observation. Patients assessed as low-risk or low-confidence prediction by CLL-TIM will only be followed by medical record review and/or registries for infections, CLL treatment and survival.

4.1.2 Medical History

Collect and record the subject's complete history through review of medical records and by interview, in particular previous infectious events and medical as well as pathology diagnoses will be collected. Concurrent medical signs and symptoms must be documented to establish baseline severities. A disease history, including the date of initial diagnosis and list of all prior treatment, in particular antimicrobial and anticancer treatments, and responses and duration of response to these treatments, will also be recorded.

4.1.3 Adverse Events

An adverse event (AE) is any untoward medical occurrence in a patient or clinical study subject administered a medicinal product and which does not necessarily have a causal relationship with the treatment.

An AE can therefore be any unfavorable and unintended sign (including an abnormal laboratory finding), symptom, or disease temporally associated with the use of a medicinal (investigational) product, whether or not related to the medicinal (investigational) product.

Only information about AE's > grade 1 will be collected, unless the AE qualifies as an AESI or a SUSAR as detailed below.

Adverse event of special interest (AESI)

Atrial fibrillation, ventricular arrhythmias, tumor lysis events, infections, disease progression, treatment for CLL, malignancies and bleeding events are adverse events of special interest in this trial and will be actively requested for.

Serious adverse event (SAE)

A serious adverse event is defined as any untoward medical occurrence or effect that at any dose:

- Results in death
- Is a life-threatening event (i.e. the patient was at immediate risk of death at the time the reaction was observed)
- Requires hospitalization or prolongation of an existing hospitalization
- Results in significant or persistent disability or incapacity

- Is a congenital anomaly or birth defect
- Is an important medical event (i.e. important adverse events that are not immediately life threatening or do not result in death or hospitalization but may jeopardize the patient or may require intervention to prevent one of the above characteristics/consequences, including suspected transmission of infectious agents by a medicinal product).

Note: Clinical TLS is *an important medical event* in this trial which must be reported as SAE. SAEs must be reported to the sponsor through the eCRF system, which automatically notifies the sponsor, within 24 hours of awareness. The sponsor must notify within the defined timelines health authorities and the companies providing investigational drugs according to EU regulations.

Suspected unexpected serious adverse reaction (SUSAR)

All **suspected** Adverse Reactions which occur in the trial and that are both **unexpected** and **serious**.

Suspected adverse reactions (AR) are those AEs of which a reasonable causal relationship to any dose administered of the investigational medicinal product and the event is suspected. Unexpected adverse reactions are adverse reactions, of which the nature, or severity, is not consistent with the applicable product information (e.g. Investigator's Brochure for an unapproved IMP or Summary of Product Characteristics (SPC) for an authorized medicinal product).

4.1.4 Severity

Definitions found in the CTCAE version 5 or higher will be used for grading the severity (intensity) of AEs. The CTCAE displays Grades 1 through 5 with unique clinical descriptions of severity for each referenced AE. Should a subject experience any AE not listed in the CTCAE, the following grading system should be used to assess severity:

- Grade 1 (Mild AE) experiences which are usually transient, requiring no special treatment, and not interfering with the subject's daily activities
- Grade 2 (Moderate AE) experiences which introduce some level of inconvenience or concern to the subject, and which may interfere with daily activities, but are usually ameliorated by simple therapeutic measures
- Grade 3 (Severe AE) experiences which are unacceptable or intolerable, significantly interrupt the subject's usual daily activity, and require systemic drug therapy or other treatment

- Grade 4 (Life-threatening or disabling AE) experiences which cause the subject to be in imminent danger of death
- Grade 5 (Death related to AE) experiences which result in subject death]

